## **ABSTRACT.**

**Background:** Percutaneous electrotherapy is today a therapeutic alternative in musculoskeletal conditions. In that sense, percutaneous microelectrolysis (MEP) stands out as treatment for tendinopathies and musculoskeletal pain, such as myofascial trigger points (MTrPs), although more studies are needed to support it.

**Objective:** Investigate effectiveness of MEP in reducing painful pressure threshold (PPT) and pain intensity (PI) in MTrPs.

**Method:** Controlled randomized clinical trial. Research was performed at Physiotherapy Laboratory of Andrés Bello University. Participants were forty-eight volunteers with MTrPs presence in upper trapezius muscle. Both groups received a baseline ultrasound treatment, adding MEP to experimental group. Intervention consisted of a MEP intervention and tree

reevaluation sessions (at day one, three and seven). Direct current was delivered with acupuncture needle directly to MTrP and PPT and PI was reevaluated before and after application. Main outcomes were PPT and PI differences (PPTdiff and PIdiff) between evaluation sessions.

**Results:** MEP demonstrated positive changes increasing PPT (PPTdiff1-1, p=0,0000, PPTdiff2-1, p=0,0000, PPTdiff3-1, p=0,0000) and decreasing PI (PIdiff1-1, p=0,0001, PIdiff2-1, p=0,0001, PIdiff3-1, p=0,0008) in experimental group, and significant differences in PPT at second reevaluation session compared to control group (PPTdiff2-1, p=0,0032).

**Conclusion:** MEP is a good analgesic treatment for MTrPs compared to therapeutic ultrasound, although neither of two therapies seems to be better than other in long term. Two treatments improvements PPT and PI, so MEP can be considered as an effective alternative treatment for MTrPs pain.

**Keywords:** electrotherapy; electrolysis; pain threshold; myofascial pain syndromes; analog visual scale.

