sex (%) men women	11 (22,9%) 13 (27,1%)	12 (25,0%) 12 (25,0%)	p = 0,7730*	Normal *
Age (mean, +/- DS)	22,5 +/- 1,9	22,0 +/- 1,6	p = 0,2993**	Normal **
BMI (Kg/m2) (mean +/- DS)	24,5 +/- 3,4	22,9 +/- 2,3	p = 0,0616**	Normal **
Short trapezius muscle laterality (%) right left	17 (70,8%) 7 (29,2%)	20 (83,3%) 4 (16,7%)	p = 0,2470***	Normal ***
SP-AC distance (cm) (mean +/- DS)	9,2 +/- 1,8	8,4 +/- 1,7	p = 0,1241**	Normal **
PPTpre 1 (Kg/cm2) (mean +/- DS)	1,4 +/- 0,2	1,4 +/- 0,2	p = 0,5734**	Normal **
PIpre1 (mm) (mean +/- DS)	32,1 +/- 13,6	31,4 +/- 15,1	p = 0,8729**	Normal **

**Table 1. Characterization of study groups.** Variable sex and short trapezius muscle laterality is represented in frequencies (%). Values for continuous variables are in means with their corresponding standard deviation (DS). Variable sex was analyzed using  $\chi^2$  test\*. For the analysis of continuous variables, the T-Student test was used\*\*. Variable short trapezius laterality was analyzed with the F-Fishertest\*\*\*.

**BMI:** body mass index, **SUTL:** short upper trapezius muscle laterality, **SP-AC distance:** distance spinous process from C7 to acromion, **PPTpre:** pain pressure threshold pre intervention at day one, **PIpre:** pain intensity pre intervention at day one. ***p* > 0,05\*\*\*\***

Secondary variables as short upper trapezius muscle laterality (SUTL) and sex were represented as frequencies, while MTrP location distance (MLD) and age was represented as median and BMI in averages. Primary variables included PPT and PI pre-intervention

(PPTpre and PIpre) were expressed as averages with their corresponding standard deviation (x, SD). Data were analyzed to compare homogeneity of groups with STATAv.13 program.

*Equipment.* GYMNA's COMBI 500 electric stimulator was used for ultrasound application at 1MHz, 1.5Watts/cm^2, 100% duty cycle, 5cm^2 ERA and 15 minutes. SVELTIA's DC equipment was used for MEP application. It was used a dispersing electrode (area 28.26cm^2) and an acupuncture needle (0.3x25millimeters). Circuit was closed by placing dispersing electrode in contralateral arm to trapezius muscle to be treated. Current intensity was 600μA at the needle (current density of 1.71mA/cm^2).

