##### 6. Pain pressure threshold (PPTpre) and pain intensity (PIpre) postintervention evaluation.

Completing intervention, participants returned to evaluation station. Evaluator repeated the same assessment protocol made before ultrasound and MEP application, recording PPT and PI postintervention. Variables PPTdiff1-1 and PIdiff1-1 were created based on differences

between algometry and pain intensity measurements before and after intervention. Participants were cited for a reevaluation on day three and seven obtained variables PPT2, PI2, PPT3 and PI3. This allowed to create PPTdiff2-1, PPT3-1, PI diff2-1 and PI diff3-1 variables, that represented differences obtained between the measurements of days three and seven with those obtained on day one before intervention.

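### Six main-outcome differences have no ranked efficacy endpoint or time point, and one between-arm result (PPT on day 3) carries a broad comparative conclusion; separately, the objective states the PPT benefit in the wrong direction

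*Protocol*

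**What the plan says.** **Main outcomes.** The Abstract (Method) states "Main outcomes were PPT and PI differences" between evaluation sessions. Procedure section 6 (postintervention evaluation) defines them. On day 1, "Variables PPTdiff1-1 and PIdiff1-1 were created based on differences" between the measurements before and after the intervention. For days 3 and 7 against the day-1 baseline, "This allowed to create PPTdiff2-1, PPT3-1, PI diff2-1 and PI diff3-1 variables".

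**Primary label.** The word is used once for outcome measures, in the text below Table 1: "Primary variables included PPT and PI pre-intervention". It describes baseline values, not an efficacy endpoint.

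**Results.** The Abstract lists six p-values for the experimental group, three for PPT and three for PI. For the comparison with control it gives one result: "significant differences in PPT at second reevaluation session compared to control group", namely PPTdiff2-1, p=0.0032.

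**Conclusion.** The Abstract judges MEP favourably for pain relief relative to therapeutic ultrasound. It adds that neither therapy appears superior in the long term and that both improve PPT and PI.

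**Direction.** The Objective is "Investigate effectiveness of MEP in reducing painful pressure threshold (PPT) and pain intensity (PI) in MTrPs". The Results say "MEP demonstrated positive changes increasing PPT".

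**The concern.** There are two separate defects.

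1. With six co-equal main outcomes and no ranking, the document does not fix which between-arm result decides whether MEP worked. A reader cannot tell whether day-3 PPT was the planned test or was picked out because it was positive. If each contrast is judged at 0.05, the chance of some positive main result is well above 5%. One result, for one measure at one time, then supports a conclusion about analgesia in general.

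2. The objective names a fall in PPT as the effect sought, while the results count a rise as success. The stated aim and the stated evidence of benefit point in opposite directions.

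At stake are the p-value quoted for the comparison, the breadth of the conclusion and the clarity of the aim. The direction error does not cause the reliance on one contrast, and it does not alter a two-sided p-value.

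**Working it through.** **Inputs**
- Measures: 2 (PPT, PI), Abstract, Method.
- Times: 3 (day 1 after the intervention, day 3, day 7, each against the day-1 baseline), Procedure section 6.
- Contrasts: 2 x 3 = 6.
- Reported between-arm p for an outcome: 0.0032 (Abstract, Results). It cannot be recomputed, because no means or SDs of the differences are given.
- Arm sizes: 24 and 24 (Procedure section 2).
- Assumed: all six contrasts are tested between arms, two-sided, at 0.05. The document gives no level for the outcomes; 0.05 appears only in the Table 1 notes.

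**Familywise error over six tests**
- Independent: 1 - 0.95^6 = 1 - 0.7351 = 0.265.
- Upper bound: 6 x 0.05 = 0.30.
- Equally correlated normal statistics (simulation, correlation assumed):

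| Correlation | Familywise error |
|---|---|
| 0.3 | 24.1% |
| 0.5 | 20.7% |
| 0.7 | 16.4% |
| 0.9 | 10.8% |

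**Adjusting the reported result**
- Bonferroni threshold: 0.05/6 = 0.0083, and 0.0032 is below it.
- Adjusted p: 6 x 0.0032 = 0.0192. Holm gives the same value if this is the smallest of the six, and no more than this otherwise.
- Under the null, the chance that the smallest of six p-values is 0.0032 or less is 1.9% if independent, falling to 0.9% at correlation 0.9.
- If 0.0032 were one-sided, the two-sided value is 0.0064 and 6 x 0.0064 = 0.0384, still below 0.05.
- If the six listed experimental-group tests are added to the family: 12 x 0.0032 = 0.0384. Only a family of 18 (six between arms plus six within each arm, assumed) takes it above 0.05: 18 x 0.0032 = 0.0576. The within-arm tests do not answer the comparative question, so six is the relevant family.

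**What the reported results cover**
- The six experimental-group p-values are changes within one arm. They do not compare the arms.
- Between arms, the document reports PPT on day 3. It reports no PI difference at any time, and no PPT difference on day 1 or day 7.
- Procedure section 4 gives ultrasound to both arms and MEP additionally to one. The contrast is therefore MEP added to ultrasound against ultrasound alone, not MEP against ultrasound.

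**Direction**
- Objective: reduce PPT.
- Results: an increase in PPT is the positive change.
- Procedure section 3: a PPT below 3 Kg/cm2 counts as a positive trigger point, so a low threshold is the abnormal state. Two places agree that higher is better; the Objective stands alone.

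**The case against.** The strongest reply is that multiplicity does not overturn the reported result. At 0.0032 it passes a six-fold correction, and the 16% to 26% figures concern any p below 0.05, not one this small. That stands. A reader might infer that the day-3 difference is merely the best of six chance results; the arithmetic does not support that.

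Second, several premises are inferred. Six variables are defined, but nowhere does the document say that six between-arm tests were run, at what level, or without adjustment. A statistical analysis plan may deal with adjustment and is not at hand. This also stands, so the error rates above are conditional. What remains is that the document itself names the main outcomes, ranks none of them, and draws a comparative conclusion.

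Third, the conclusion already carries a long-term caveat, which fits a difference seen only on day 3. The caveat limits the claim in time. It does not tell the reader that only one of six contrasts is reported as different, or that no PI difference is.

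Fourth, naming a primary contrast now, with results known, would repeat the selection problem. That is correct and shapes the fix.

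Finally, a reader might take silence on the other five contrasts to mean that they were not significant, or read the PPT gains as failures of the objective. Neither is supported. No between-arm results are given for those five, and the trigger-point criterion shows that the objective is misworded, not that the benefit was misjudged.

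**Conclusion.** Both defects hold, in limited form.

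1. The document ranks no efficacy endpoint or time point among six main-outcome differences and mentions no multiplicity adjustment. If all six are tested between arms at 0.05, the familywise error is 26% under independence and about 16% to 24% for assumed correlations of 0.7 down to 0.3. The day-3 PPT result remains significant after adjustment over six (0.019 instead of 0.0032). What it does not support is a general statement of analgesic merit relative to ultrasound: it concerns one measure on one day, for MEP added to ultrasound.

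2. The objective contradicts both the Results and the trigger-point criterion on the direction of PPT. This is a wording error with no effect on a two-sided test.

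The verdict rests on the assumed 0.05 level, two-sided testing and a family of six.

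**What to change.** - Use a single primary between-arm contrast only if a dated record shows that it was chosen before the data were seen.
- Otherwise treat the six between-arm contrasts as one family with Holm adjustment. Report all six estimates with confidence intervals and adjusted p-values, and state the significance level and sidedness. Day-3 PPT then reads 0.019 instead of 0.0032 (taking 0.0032 as two-sided and the smallest of the six).
- Limit the conclusion to PPT on day 3 for MEP added to ultrasound, unless the other contrasts support more. Do not describe the other five as non-significant unless their results show it.
- Correct the objective to increasing PPT and reducing PI.

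The cost is some rewording, one adjustment and the reporting of contrasts from measurements already collected. The quoted p-value becomes less favourable and the conclusion narrower. Power per contrast also falls. With 24 per arm, the standardised difference detectable with 80% power is (1.960 + 0.842) x sqrt(2/24) = 0.81 at 0.05, and (2.638 + 0.842) x sqrt(2/24) = 1.00 at 0.05/6, Holm's strictest step. This is a further reason to show intervals for all six.

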## **Material and Methods**

Present design represents a randomized double-blind clinical trial. Study was approved on June 18, 2019 by Eastern Metropolitan Health Service of Santiago (SSMO) ethics committee. Study was registered at [www.clinicaltrials.gov](http://www.clinicaltrials.gov). Participants were divided in two groups assessed in both presences of MTrPS in shorter upper trapezius muscle. It was recording the PPT and PI before and after intervention. Both groups received therapeutic ultrasound as baseline treatment. Experimental group received microelectrolysis additionally. A reassessment of PPT and PI was done on day one, three and seven post intervention.

*Subjects.* forty-eight healthy volunteers were recruited (23 men, 25 women, average age 22 years). Participants were students of Science Rehabilitation Faculty (SRF) of Andrés Bello University, Santiago de Chile. Number of participants was selected by convenience. An invitation was extended to students through formal communication channels (mailing), student representatives and social networks, summoning two hundred and seven potential participants. Selection was based on a survey whose first part was structured in relation to general demographic participant's data, including name, age, sex, body mass index (BMI), career year, and personal information contact (e-mail and cell phone number). Second part of survey consisted of closed questions constructed by eligibility criteria. Inclusion criteria considered participants over 18 years old, students of SRF and positive hypersensitive MTrPs. Exclusion criteria include neck or shoulders pathologies in the last 6 months (as fractures, sprains, tendinopathies, dislocations or muscle tears), cervical pain, sensitivity alterations such as hypesthesia, anesthesia or hyperesthesia in neck, shoulders and/or arms, wounds or skin alterations in shoulder as psoriasis, scars or keloids, fear to electrotherapy application and analgesic pharmacological treatment at recruitment time (non-steroidal anti-

inflammatory or steroidal drugs). Elimination criteria considered non-tolerance electrotherapy intervention and non-completion of evaluation protocol (attendance at all scheduled sessions). Demographic data were tabulated in Microsoft excel® 2016 program (Table 1, characterization of study groups).

Variable	MEP (n = 24)	Control (n = 24)	p-value	Sample distribution

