**Figure 1. Subject recruitment and flow through the study**

## 2. Groups.

Sample was divided by a simple randomization process performed with a random number table, assigned participants to one of two study groups. Sequence of randomization and participants of each group was only known by principal investigator. Working groups were designated as experimental (MEP group, n = 24) and control group (n = 24). None subjects knew the treatment that would be applied. Each participant was evaluated registering their age, BMI and SUTL. Location of MTrP was determined at shortness trapezius muscle, taking as reference a line between superior acromion's midpoint surface and C7 spinous process (PE-AC distance). Algometry and VAS was subsequently applied obtaining the PPT and PI

pre intervention (PPTpre y PIpre). Variables described were compared between groups to assess the homogeneity of them (Table 1). Data reflect the homogeneity of groups at the beginning of the study.

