### 4. Therapeutic ultrasound application.

Participants of both groups received a therapeutic ultrasound treatment. Experimental group received first ultrasound and subsequently MEP, while control group was treated only with ultrasound. Ultrasound intervention protocol was performed in the same way for both groups. Application was performed in an adjoining room by another physiotherapist who didn't know

groups. Treatment was carried out with participant in sitting position applying ultrasound at sensitive point marked by examiner of evaluation station. Ultrasound therapy was delivery at 1MHz, 1.5 Watts/cm^2, 100% duty cycle (SATP: 1.5Watts/cm^2 and SATA:1.5W/cm^2), ERA 5cm^2 and 15 minutes. Once ultrasound intervention was finished, participants of MEP group were taken to microelectrolysis box, while participants of control group returned to evaluation station.

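### The conclusion ranks MEP against ultrasound, but the two arms compare ultrasound plus MEP with ultrasound alone

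*Protocol*

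**What the plan says.** The design is described the same way throughout the Protocol. The Abstract's Method states: "Both groups received a baseline ultrasound treatment, adding MEP to experimental group". Material and Methods repeats it: "Both groups received therapeutic ultrasound as baseline treatment. Experimental group received microelectrolysis additionally". Procedure, section 4, gives the order: "Experimental group received first ultrasound and subsequently MEP, while control group was treated only with ultrasound", and adds that the ultrasound protocol did not differ between groups. Procedure, section 2, gives two arms: "Working groups were designated as experimental (MEP group, n = 24) and control group (n = 24". On sample size, Material and Methods says only: "Number of participants was selected by convenience".

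The Abstract's conclusion makes three statements:

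- a comparison: "MEP is a good analgesic treatment for MTrPs compared to therapeutic ultrasound";
- a statement of parity: "although neither of two therapies seems to be better than other in long term";
- an inference: "Two treatments improvements PPT and PI, so MEP can be considered as an effective alternative treatment for MTrPs pain".

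The Abstract's results report small p-values for change from day one within the experimental group. They report one significant difference between groups, for PPTdiff2-1 (p = 0.0032), which by Procedure, section 6, is the day-three change. No between-group result for day seven or for pain intensity is given in the text available.

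**The concern.** The conclusion treats MEP and ultrasound as two separate options that were tested against each other. The trial tested whether MEP adds anything once ultrasound has been given. These questions can have different answers from the same data.

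The difference matters most if the contrast was null at the last visit. Under the design, a null contrast means that adding MEP brought no demonstrated gain over ultrasound alone. The conclusion reads it as two therapies of similar worth and goes on to call MEP an effective alternative. A reader could then use MEP in place of ultrasound, which no participant received. The last assessment is day seven, so the long-term statement rests on one week of follow-up.

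The statement that both treatments improve PPT and pain intensity has a related weakness. It rests on change from day one within arms that have no untreated or sham comparator.

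**Working it through.** **1. Which contrast the arms identify.** Let T be the change that would occur without either treatment (time, retesting, expectation), U the effect of ultrasound and M the effect of MEP. Assume first that the effects add.

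| Arm | n | Expected change from day one |
|---|---|---|
| Experimental | 24 | T + U + M |
| Control | 24 | T + U |

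- Randomised contrast: (T + U + M) − (T + U) = M, the added effect of MEP.
- Contrast claimed in the conclusion: M − U.
- U appears only in the sum T + U and is never separated from T. M − U therefore cannot be recovered.
- If the effects do not add, with interaction I, the contrast becomes M + I. That is the effect of MEP given ultrasound, and M − U is no nearer.

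**2. What a null contrast would imply.** Suppose the true day-seven contrast were zero. Under additivity, M = 0. Parity of the two therapies (M = U) would then require U = 0 as well, so that neither treatment had any effect at day seven. That does not fit a conclusion that both improve PPT and pain intensity.

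**3. Within-arm changes.** The experimental-arm p-values test T + U + M = 0, and a control-arm test would concern T + U = 0. Neither isolates U or M, so they support a before-after description only.

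**4. Whether 24 per arm could support equality of the two regimens.** The Protocol states no power, effect size or margin, so there is no figure of its own to reproduce. Assume an unpaired two-sided t-test, alpha 0.05, 46 degrees of freedom.

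- 95% half-width = t(0.975; 46) × √(2/24) = 2.013 × 0.2887 = 0.581 SD of the change score.
- Power for a true difference of 0.5 SD: 0.396.
- Difference detectable with 80% power: 0.826 SD.

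**5. The half-width in the units of measurement.** The SD of change is not given. As an assumption, take the follow-up SD equal to the baseline SD in Table 1, with pre-post correlation r from 0.2 to 0.8, so that SD of change = SD × √(2(1 − r)).

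Pain intensity: pooled SD = √((13.6² + 15.1²)/2) = 14.37 mm; mean baseline = (32.1 + 31.4)/2 = 31.75 mm. PPT: SD 0.2 and mean 1.4 Kg/cm² in both arms.

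| r | PI: SD of change | PI: half-width | % of baseline | PPT: SD of change | PPT: half-width | % of baseline |
|---|---|---|---|---|---|---|
| 0.2 | 18.18 mm | 10.6 mm | 33% | 0.253 | 0.147 | 10.5% |
| 0.5 | 14.37 mm | 8.3 mm | 26% | 0.200 | 0.116 | 8.3% |
| 0.8 | 9.09 mm | 5.3 mm | 17% | 0.126 | 0.073 | 5.2% |

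**6. The one reported between-group result.** If p = 0.0032 came from the same t-test, then t = 3.11 and the standardised difference is 3.11 × 0.2887 = 0.90 SD. It estimates the day-three effect of adding MEP to ultrasound.

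**The case against.** The strongest reply is that the conclusion uses shorthand. Procedure, section 2, and Table 1 call the ultrasound-plus-MEP arm the MEP group, so a comparison of MEP with ultrasound could mean that group against control. The Abstract's own Method also describes the add-on. This reading could rescue the first statement taken alone. It does not rescue the next two, which speak of two therapies and two treatments and so set MEP and ultrasound side by side as separate options. The objection does establish that ultrasound must remain in the restated sentence as the comparator.

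A second reply is that alternative may mean only an available option, as in the Abstract's background, and that the parity statement is hedged and sets no equivalence margin. Both points are fair as to wording. But the word alternative is drawn as an inference from both treatments having improved the outcomes, which within-arm changes cannot show. Hedging does not alter which contrast was estimated.

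Third, the precision figures rest on assumptions, and showing pain intensity alone would overstate the relative imprecision. That is correct. PPT is shown beside it, and its half-width is about 5% to 10.5% of baseline. The identification argument needs none of these figures.

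Two further points stand but do not affect the finding. The between-group results for day seven and for pain intensity are not visible here, so any statement about them must be conditional. The Abstract's objective speaks of reducing PPT while its results count an increase as favourable. That is a separate wording matter; the objective is compatible with an add-on design.

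**Conclusion.** The concern holds. The sections describing the design agree, and 0 of 48 participants received MEP without ultrasound. The trial can support, or fail to support, a gain from adding MEP to ultrasound. It cannot rank the two therapies or show that they are equal. This follows from the content of the arms and needs no distributional assumption.

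The precision argument is secondary and rests on an assumed unpaired t-test at two-sided 0.05. On that basis a half-width of 0.58 SD and power of about 40% at 0.5 SD mean that a non-significant difference would not establish equality even of the two regimens actually compared. The figures in millimetres and Kg/cm² also depend on the assumed correlation and follow-up SD.

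The add-on design itself is legitimate. The fault lies in the conclusion drawn from it.

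**What to change.** In the Abstract's conclusion, and wherever the full report repeats it:

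- State the finding as the effect of adding MEP to ultrasound, compared with ultrasound alone.
- Remove the wording that sets MEP directly against ultrasound, the statement that neither therapy is better, and the description of MEP as an alternative treatment.
- Report the between-group PPT difference at the second reevaluation (p = 0.0032) as an add-on effect, with its direction, size and 95% confidence interval from the full results.
- For day seven, and for pain intensity, give the between-group difference with its confidence interval. Write that no added benefit was demonstrated only where the full results show a non-significant difference, and name day seven in place of the long term.
- Describe within-arm results as changes from day one, not as effects of ultrasound or of MEP.

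No new arm or data are needed, only rewording and between-group estimates from measurements already taken. The price is a narrower claim: nothing can be said about MEP used in place of ultrasound.

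### The Conclusion calls MEP an effective alternative because both arms improved, although both arms had ultrasound and none had MEP alone; its long-term statement rests on seven days

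*Protocol*

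**What the plan says.** The design is stated consistently in three places. The Abstract (Method) says "Both groups received a baseline ultrasound treatment, adding MEP to experimental group". Material and Methods repeats it: "Experimental group received microelectrolysis additionally". Procedure, item 4, gives the order: "Experimental group received first ultrasound and subsequently MEP, while control group was treated only with ultrasound". There are two arms of 24 (Procedure, item 2).

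Both arms were measured in the same way. Procedure, item 6, says "Evaluator repeated the same assessment protocol made before ultrasound and MEP application, recording PPT and PI postintervention", with further visits on days 3 and 7. Changes are taken from the pre-intervention values of day 1, for pain pressure threshold (PPT) and pain intensity (PI).

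The Results part of the Abstract gives seven p-values. Six are changes within the experimental arm, three for PPT and three for PI; the PI ones read "decreasing PI (PIdiff1-1, p=0,0001, PIdiff2-1, p=0,0001, PIdiff3-1, p=0,0008) in experimental group". The seventh is the only comparison between arms: "significant differences in PPT at second reevaluation session compared to control group (PPTdiff2-1, p=0,0032").

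The Conclusion first calls MEP good by comparison with ultrasound. It then adds that "neither of two therapies seems to be better than other in long term" and ends with "Two treatments improvements PPT and PI, so MEP can be considered as an effective alternative treatment for MTrPs pain".

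**The concern.** The last sentence of the Conclusion makes improvement in both arms the reason for calling MEP effective. That is a within-arm argument, and here it cannot isolate MEP. Ultrasound, natural course and repeated algometry act in both arms. So does regression to the mean, which is plausible because the most sensitive point was sought out and a PPT below 3 Kg/cm² was required (Procedure, item 3).

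The Conclusion also writes as if two separate therapies had been set against each other. The randomised contrast is MEP plus ultrasound against ultrasound only, which estimates what MEP adds. It says nothing about MEP used in place of ultrasound.

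Finally, a statement about the long term is attached to follow-up that ends at day 7. A reader could take from this Abstract that MEP relieves pain intensity, that it can replace ultrasound, and that the two are similar over time. The between-arm evidence printed there supports none of the three.

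**Working it through.** No sample-size, power or margin calculation is stated (the number of participants was chosen by convenience), so there is no figure of the plan's own to reproduce. The calculations show how little the both-arms-improved argument discriminates, and how wide a day-7 comparison would be. The outcome tests are not named in the text, so t-tests, normal changes, equal SDs and two-sided alpha 0.05 are assumed.

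**Inputs.** 24 per arm (Procedure, item 2). Within-arm PI at day 7, p=0.0008, and between-arm PPT at day 3, p=0.0032 (Abstract). Baseline PI 32.1 ± 13.6 mm and 31.4 ± 15.1 mm (Table 1).

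**1. Could both arms improve if MEP did nothing?** The largest within-arm p-value marks the smallest effect.
- Paired t, df = 23: p=0.0008 gives t = 3.858, so d = 3.858/√24 = 0.787 SD of change.
- Power of one arm's paired test at d = 0.787 is 0.958. With the same true change in both arms and no MEP effect, both are significant with probability 0.958² ≈ 0.92.
- A simulation of 200,000 trials agrees:

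| Shared change (SD) | Both arms p<0.05 |
|---|---|
| 0.787 | 0.919 |
| 0.6 | 0.646 |
| 0.5 | 0.423 |

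In these runs the between-arm test was positive in 0.049 to 0.050, its nominal rate.

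**2. What does the printed between-arm result support?**
- Two-sample t, df = 46: p=0.0032 gives |t| = 3.111, so |d| = 3.111 × √(2/24) = 0.898 SD.
- The 95% CI by noncentral t is 0.299 to 1.488, taking the difference to favour MEP.
- Against the first Holm threshold over six contrasts, 0.05/6 = 0.0083, p=0.0032 still passes.

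This is evidence of an added effect of MEP on PPT at day 3. The Abstract gives no between-arm result for PI.

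**3. How much could a day-7 comparison say?**
- Half-width of the 95% CI for a between-arm difference: 2.013 × √(2/24) = 0.581 SD.
- Pooled baseline PI SD: √((13.6² + 15.1²)/2) = 14.37 mm. The SD of change is 14.37 × √(2(1 − r)), where r is the assumed pre-post correlation and the baseline SD is taken to hold at day 7.

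| r | SD of change (mm) | CI half-width (mm) |
|---|---|---|
| 0.7 | 11.1 | 6.5 |
| 0.5 | 14.4 | 8.3 |
| 0.3 | 17.0 | 9.9 |

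These half-widths stand against a baseline of about 32 mm. Power with 24 per arm (normal approximation) is about 10% at 0.2 SD, 41% at 0.5 SD and 79% at 0.8 SD. A non-significant day-7 test would leave differences of moderate size open, and no equivalence or non-inferiority margin is given.

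**The case against.** The strongest reply is that this is the brief wording of an abstract. No full Results section is in the text at hand, the other between-arm contrasts may well have been run, and abstracts often name only the significant one. That is fair: the shortage of between-arm results in the Abstract is not proof that they are missing, and the direction of the day-3 difference is reasonably implied by the surrounding sentences. But no further result would make improvement in both arms a valid reason for efficacy, or supply an arm treated with MEP alone.

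The word alternative can also be read mildly, as a treatment option; the Abstract's Background uses it in that sense. On that reading the sentence still draws effectiveness from improvement in both arms, and the Conclusion still speaks of two treatments and two therapies.

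The long-term sentence is hedged, claims no formal equivalence, and sits in an Abstract that prints the visit schedule. This softens the point, but day 7 remains the last measurement.

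The 92% is an illustration. It treats the observed 0.787 SD as the true shared change, although its 95% CI under the same assumption is about 0.32 to 1.24. It also supposes that MEP adds nothing, which the day-3 result argues against for PPT; for PI the question is open.

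**Conclusion.** The concern holds. The inference from improvement in both arms to MEP as an effective alternative is invalid under the design that the document itself describes, and the long-term wording does not fit a last visit at day 7. These two conclusions rest on the stated design alone and need none of the assumed tests. The sizes do need them: the both-arms-improved criterion would be met 42% to 92% of the time with no MEP effect, for shared changes of 0.5 to 0.787 SD, and a day-7 interval would reach about 0.58 SD either side of its estimate. What survives is narrower: an added effect of MEP over ultrasound on PPT at day 3, about 0.90 SD if a two-sample t-test was used and the difference favours MEP. The error should be fixed, but it lies in the claim and does not make the trial's data unusable.

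**What to change.** - Base every effect claim on the between-arm differences in the PPT and PI change scores. Report all six (two outcomes, three times) with direction and 95% CI.
- Label the within-arm p-values as descriptive.
- Delete the inference from improvement in both arms to effectiveness.
- Describe the treatment tested as MEP added to ultrasound, and limit the claim to contrasts that hold between arms. From the Abstract alone that is PPT at day 3, once its direction is stated.
- Replace the long-term sentence with the day-7 between-arm difference and its CI.
- A multiplicity adjustment over the six contrasts is optional.

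The cost is a little reporting work and some rewording of the Results and Conclusion, with no new participants; the contrasts may already have been computed. The headline becomes less favourable to MEP.
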